1. RATIONALE

What We Know:

- Hypertension (HTN) is a major public health concern in the United States as there is wide prevalence, high cost, and poor rates of control
- Self-monitoring of blood pressure (BP) can be helpful for both treatment decisions and evaluating response to treatment
- Hand transmitted BP logs are often inaccurate, with large under-reporting of BP
- White-coat HTN and masked HTN are frequent, and are associated with adverse cardiovascular outcomes
- Evidence that telemonitoring interventions can be effective
- Team-based care including pharmacists can improve BP management
- Home BP monitoring, mobile health interventions and referrals to clinical pharmacists for BP management have all shown potential to be effective intervention strategies

What We Don't Know:

- Available evidence suggests a potential for added benefit with community pharmacists' intervention in HTN, but the true effect is uncertain due to poor study quality, inconsistent results and potential for publication bias (systematic review 2015)
- The impact of pharmacists interventions on cardiovascular disease (CVD) is not quantitatively and qualitatively known
- The impact of pharmacist counseling of adult patients with out-of-control HTN, with managing their telemonitoring blood pressure readings

2. BACKGROUND

Hypertension (HTN) places a significant burden on the health care system in the United States. Over thirty percent of adults over the age of 20 are either taking an antihypertensive agent and/or have hypertensive blood pressure (BP).¹ It is well-known that the risk of cardiovascular disease (CVD) is increased in patients with high blood pressure. Additionally, in 2015, the number of deaths from essential hypertension and hypertensive renal disease was 32,200 or 10 of every 100,000 people in the general population and physicians saw over 42.7 million patients with diagnosed hypertension.^{2,3}

In 2017, the American College of Cardiology (ACC) and the American Heart Association (AHA) Task Force on Clinical Practice Guidelines released a guideline that calls for tighter blood pressure control in hypertensive patients. By this guideline, blood pressure above 130/80 mmHg requires treatment with medications for patients who are at high risk for cardiovascular disease.⁴ However, the guideline also heavily focuses on non-pharmacological interventions, which play an important role in blood pressure reduction. Recommendations include weight loss for those who are overweight or obese, adopting a heart-healthy diet, sodium reduction, potassium supplementation for those who have increased blood pressure or hypertension, increased physical activity, and limitation of alcohol consumption.

Besides lifestyle modifications, the guideline also places an increased emphasis on self-monitoring of blood pressure. Although there is currently limited evidence to show blood pressure reduction for patients who measure blood pressure at home, the authors of the guideline comment on its benefit because of inconsistencies between home and in-office readings. Home blood pressure monitoring also provides immediate feedback to patients on control.⁵ In a systematic review regarding self-monitoring of blood pressure, it was found that self-monitoring of BP worked best when combined with more intensive interventions, such as lifestyle counseling.⁶

Telemonitoring, also known as telemedicine, is defined as the use of health informatics, disease management, and home telehealth technologies to enhance the health of individuals and populations. Results with using remote blood pressure monitors are mixed, however the 2017 ACC/AHA guideline recommends telehealth strategies as useful adjuncts for blood pressure control.^{7,8} It is surmised that the mixed results for telemonitoring may be dependent on the extent of patient education and involvement in using the devices.

Pharmacists, working alongside other healthcare providers can help reduce blood pressure in patients with hypertension.⁹ Clinical pharmacists can instruct patients on lifestyle modifications, proper blood pressure measurement techniques and medication management. Several studies have shown the benefit of web-based pharmacist care with home blood pressure monitoring for improvement of blood pressure in a clinic setting.^{5,10,11} Pharmacists providing lifestyle counseling to patients with hypertension have also helped patients lower their blood pressure more than patients without pharmacist's counseling, as well as improving patient quality of life.^{12,13} Because of the strong evidence showing improvement in blood pressure with interventions by both ambulatory care and community pharmacists, collaboration between pharmacists across practice settings may also be beneficial, however further research is needed to demonstrate this.¹⁴

3. STUDY OBJECTIVES

Primary Objective

- To produce preliminary data to design a larger, funded study

Secondary Objectives

- To assess patient comfort in using home telemonitoring for blood pressure combined with pharmacist counseling and monitoring using a survey instrument with a Likert scale
- To assess the ability to collect and monitor hypertension data using Bluetooth enabled mobile health technology
- To determine if blood pressure readings improve with pharmacist interventions

4. STUDY DESIGN

This is a pragmatic before and after trial with the patient serving as their own control

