5. STUDY POPULATION

We are aiming to enroll 20 patient participants for this pilot study. To be eligible for participation, enrollees must be ≥ 18 years old, have a smartphone compatible with the mobile intervention, have been previously diagnosed with hypertension, have uncontrolled hypertension (SBP > 130 mmHg and/or DBP > 80 mmHg), be under the care of a primary care physician in the Family Medicine

Department of the USF Morsani Center for Advanced Care, have had at least one prescription filled at Pharmacy Plus within the last six months, and speak English fluently.

Patients will be excluded if they are already under the care of a clinical pharmacist in the Family Medicine department, are pregnant, or have a serious existing medical condition(s) that may affect their ability to self-monitor their blood pressure (for example, stroke, dementia).

Recruitment

A list of potential patients (Family Medicine patients with diagnosis of hypertension who have had at least one prescription filled at Pharmacy Plus within the last 6 months) will be generated by the Epic support team and identified through the electronic medical records system as well as the pharmacy prescription database. The pharmacists from Pharmacy Plus on this study or 4th year pharmacy students on their Ambulatory Care or Community Pharmacy Rotation will call patients on this list and will discover if the patient meets the final qualification for the study (has a smart phone or other smart device) and is interested in being a part of the study. This is not cold calling, as this list includes eligible patients who have had a prescription filled at Pharmacy Plus within the last 6 months. Each patient on this list has interacted with the pharmacists at Pharmacy Plus when the medication was dispensed. The pharmacists have an established relationship with these patients, as they are involved with the care of these patients. They are involved with the treatment of these patients as they provide pharmacy services when dispensing medications and counseling the patients, as well as some medical services such as vaccine administration.. [name], who practices in the Family Medicine department, is the physician on this study and is aware that these patients will be contacted via phone. We will not be obtaining verbal consent to participate during this phone call.

Enrollment

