6. INTERVENTIONS

Devices

- Smart Phones with Apple Health Software will be used to monitor blood pressure once a day, and results will be sent automatically to the patients EHR (Epic)
- The Omron 10 Series Wireless Upper Arm Blood Pressure Device will be given to the patient to monitor blood pressure at home daily

Pre- and Post-surveys

- A pre- and post-survey will be given at the initial and final in-person appointments, respectively
- These surveys will collect basic patient demographics, knowledge of blood pressure, comfort with checking blood pressure at home, and previous experience working with a pharmacist

Pharmacist Management

- Review of evidence-based therapy and recommendations for improvement if needed
- Educate the patients on how to monitor their blood pressure with their Bluetooth enabled home blood pressure monitor and smart phones

- Patients will be scheduled for a one-hour in-person appointment for the initial study visit where informed consent will be obtained, and for the final study visit
 - At the final study visit, the patients will complete a post-study survey and be given a \$25 gift card upon return of the blood pressure device
- Review results once per week
 - If any patient has an SBP reading > 160 mmHg or DBP > 100 mmHg, they will be instructed to wait five minutes and then recheck their BP. If the BP readings exceed these thresholds for three days in a row, the patients should contact their primary care provider in the clinic for further management.
 - If SBP > 180 mmHg and/or DBP > 120 mmHg, patients will be instructed to call 911 or have someone drive them to the ER immediately
 - There will not be alerts sent to the study pharmacists if the blood pressure readings are above these thresholds
- Follow-up with patients once per week for six (6) weeks via scheduled 20-minute telehealth appointment with each patient via the HIPAA secure and compliant platform, VSee
 - During this telehealth appointment, the study pharmacists will counsel the patients on their blood pressure readings for that week and provide lifestyle education focusing on patient-specific diet and exercise recommendations
- The total duration of the study will be eight (8) weeks

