11. DATA MANAGEMENT AND ANALYSIS

- Primary Objective: Preliminary data to design a larger, funded study
 - Captured data and information will be collected in such a way as to make it useful for putting forth a cogent argument for a larger effort.
- BP readings will be captured automatically in Epic
- Mean BP readings will be calculated and compared for the pre- and post-periods, as will the number of patients in and out of blood pressure control
- Pre- and post-study data will be analyzed using a comparison of means (2-tail t-test) and chi-square for comparing low compliant patients (for using the devices) with high compliant patients. The post-study patient satisfaction data will be analyzed using descriptive statistics.

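### With no record of antihypertensive changes, the before-after BP comparison cannot separate physician-made drug changes from the effect credited to the pharmacists

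*Combined protocol and SAP*

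**What the plan says.** Section 4 defines the design in one sentence: "This is a pragmatic before and after trial with the patient serving as their own control". There is no concurrent control. Section 11 gives the analysis: "Mean BP readings will be calculated and compared for the pre- and post-periods", together with the number of patients in and out of control, using a two-tailed t-test for means. Section 3 lists, as the last of three secondary objectives, whether BP improves with the pharmacists' interventions. Section 7 expects a significantly greater proportion in control afterwards, at p < 0.05.

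On drug treatment, the only entry condition in Section 5 is that patients "have had at least one prescription filled at Pharmacy Plus within the last six months". Entrants must be above 130 mmHg systolic and/or 80 mmHg diastolic. They must also "be under the care of a primary care physician in the Family Medicine" department, so ordinary care continues. The exclusions begin "Patients will be excluded if they are already under the care of a clinical pharmacist in the Family Medicine department, are pregnant" and end with serious conditions that affect self-monitoring. None concerns a recent antihypertensive change.

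Section 6 gives two routes by which treatment may change during the study. The pharmacist reviews therapy and may recommend improvements. If high readings persist for three days, "the patients should contact their primary care provider in the clinic for further management".

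**The concern.** A patient is a fair control for himself or herself only if other causes of a systematic BP change are absent or can be identified. Here one such cause is foreseeable. A drug started or increased by the physician shortly before enrolment may still be lowering BP after the baseline reading. A physician may also change treatment during the eight weeks for reasons that have nothing to do with the study. Either fall enters the post-period mean and the control count, and the plan has no means of identifying it.

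What is at stake is attribution. The primary objective is preliminary data for a larger, funded study. If BP-lowering changes of this kind occurred, the pilot's BP result would look better than the programme deserves, and those planning the next study could not say by how much.

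**Working it through.** **Text check.** The available sections were read for four provisions:

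- A stable-regimen entry criterion: none in Section 5.
- A run-in or a defined pre-period: none. No available section says which readings form the pre-period or when they are taken.
- A record of antihypertensive changes with date and origin: none in Sections 6, 11 or 13.
- Adjustment, stratification or a sensitivity analysis for such changes: none in Section 11.

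The text between Sections 7 and 9 was not available, so a provision there cannot be excluded.

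**Size.** The plan gives no figure to reproduce: Section 5 says "We are aiming to enroll 20 patient participants for this pilot study" without a power calculation, effect size, SD or rate of medication change. The following is an illustration.

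Inputs:
- n = 20 (Section 5)
- f = share of patients with a relevant drug change: 10% to 30%, assumed (2 to 6 of 20 patients)
- d = SBP fall still to come after the baseline reading: 5 to 10 mmHg, assumed
- SD of the within-patient change: 8, 12 or 15 mmHg, assumed
- True pharmacist effect: zero

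Spurious fall in group mean = f × d:
- lowest: 0.10 × 5 = 0.5 mmHg
- highest: 0.30 × 10 = 3.0 mmHg

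The standard error of the mean change is about SD/√20: 8/4.47 = 1.8 mmHg to 15/4.47 = 3.4 mmHg.

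The chance of a significant two-sided paired t-test at 0.05 was simulated with 40,000 runs per cell. Section 11 does not say paired or unpaired; paired is assumed.

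| f | d (mmHg) | Mean shift (mmHg) | SD 8 | SD 12 | SD 15 |
|---|---|---|---|---|---|
| 0% | – | 0 | 0.05 | 0.05 | 0.05 |
| 10% | 5 | 0.5 | 0.056 | 0.053 | 0.053 |
| 10% | 10 | 1.0 | 0.077 | 0.060 | 0.059 |
| 20% | 5 | 1.0 | 0.079 | 0.062 | 0.059 |
| 20% | 10 | 2.0 | 0.150 | 0.103 | 0.083 |
| 30% | 5 | 1.5 | 0.116 | 0.079 | 0.071 |
| 30% | 10 | 3.0 | 0.276 | 0.163 | 0.128 |

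The false-positive rate is close to nominal at the low end (0.05 to 0.06) and reaches 0.13 to 0.28 only at the high end.

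**The case against.** The strongest reply is that much of what happens to treatment during the study belongs to the programme. Section 6 makes therapy review and recommendations part of pharmacist management, and the referral to primary care is triggered by study readings. A reader might infer that every clinic-made change during the eight weeks is bias. The documents do not support that. Changes following a pharmacist's recommendation are intervention, and those following the referral arguably are too, in a trial that calls itself pragmatic. Only changes before entry or independent of the programme remain. This part of the objection stands and sets the limits of the point.

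A reader might also infer that entrants are typically patients whose therapy has just been stepped up. Section 5 does not show this. A single fill of any drug in six months qualifies, including a routine refill, and uncontrolled BP fits long-unchanged treatment just as well.

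Three further replies have some force:

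- Unsystematic changes add variance rather than bias, and stopped or reduced drugs could push BP upwards. The bias favours the hypothesis only if the net change lowers BP.
- A longer or later baseline would absorb part of the residual effect of pre-entry changes.
- BP is a secondary outcome in a 20-patient pilot, and no available section says that the observed effect will size the larger study. Section 11 says only that the data should help argue for it.

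These replies lower the priority. They do not answer the main gap: if such changes occur, the plan holds no information with which to recognise them.

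**Conclusion.** The point holds as a limit on attribution. Under the plan as written, BP falls from physician-made antihypertensive changes before entry, or independent of the programme during it, cannot be separated from the effect that Section 3 credits to the pharmacists. The amount is unknown. The range of 0.5 to 3.0 mmHg rests wholly on assumed values of f and d, and it varies with the timing of the undefined baseline reading. It may not matter in practice, but the data needed to find out are not planned.

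A reader might go further and argue that 30% of 20 is 6 patients, and that 6 conversions to control with none lost would already give an exact McNemar p of 2 × 0.5⁶ = 0.031. That does not follow. It treats every patient with a drug change as reaching control, yet Section 5 sets no upper BP limit, and a further fall of 5 to 10 mmHg would leave many patients above 130/80 mmHg. If each of the six had an assumed 50% chance of converting, all six would do so with probability 0.5⁶ = 0.016. McNemar's test is also not named in the plan.

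The change is worth making because it is cheap and bears on what the pilot can conclude. It is not a reason to hold the study up.

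**What to change.** 1. From Epic and the Pharmacy Plus database, both already used to build the recruitment list (Section 5), extract each patient's dated antihypertensive starts, stops and dose changes from a fixed window before enrolment to the final visit.
2. Have the study pharmacists note any treatment recommendation at the weekly contacts, since the databases alone may not show who prompted a change.
3. Class each change as pre-entry, following a pharmacist recommendation, following the Section 6 referral to primary care (on its own line, as arguably part of the programme), or independent of the study.
4. Keep the all-patient result as the main one. Beside it, give the counts of changes by class and a descriptive sensitivity table of BP change and number in control among patients with no pre-entry or independent change.
5. Word the BP conclusion as change during the programme, not as an effect of the pharmacist alone.

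The cost is one extraction for 20 patients, a short note at contacts already scheduled, and one table. The subset will be small and imprecise: if 30% of patients had such a change, 20 − 6 = 14 would remain. Fills at other pharmacies may be missed, and the headline effect may look smaller. In return, the observed rate of independent changes is itself useful preliminary data. No eligibility or prescribing rule changes.

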5. STUDY POPULATION

We are aiming to enroll 20 patient participants for this pilot study. To be eligible for participation, enrollees must be ≥ 18 years old, have a smartphone compatible with the mobile intervention, have been previously diagnosed with hypertension, have uncontrolled hypertension (SBP > 130 mmHg and/or DBP > 80 mmHg), be under the care of a primary care physician in the Family Medicine

Department of the USF Morsani Center for Advanced Care, have had at least one prescription filled at Pharmacy Plus within the last six months, and speak English fluently.

Patients will be excluded if they are already under the care of a clinical pharmacist in the Family Medicine department, are pregnant, or have a serious existing medical condition(s) that may affect their ability to self-monitor their blood pressure (for example, stroke, dementia).

Recruitment

A list of potential patients (Family Medicine patients with diagnosis of hypertension who have had at least one prescription filled at Pharmacy Plus within the last 6 months) will be generated by the Epic support team and identified through the electronic medical records system as well as the pharmacy prescription database. The pharmacists from Pharmacy Plus on this study or 4th year pharmacy students on their Ambulatory Care or Community Pharmacy Rotation will call patients on this list and will discover if the patient meets the final qualification for the study (has a smart phone or other smart device) and is interested in being a part of the study. This is not cold calling, as this list includes eligible patients who have had a prescription filled at Pharmacy Plus within the last 6 months. Each patient on this list has interacted with the pharmacists at Pharmacy Plus when the medication was dispensed. The pharmacists have an established relationship with these patients, as they are involved with the care of these patients. They are involved with the treatment of these patients as they provide pharmacy services when dispensing medications and counseling the patients, as well as some medical services such as vaccine administration.. [name], who practices in the Family Medicine department, is the physician on this study and is aware that these patients will be contacted via phone. We will not be obtaining verbal consent to participate during this phone call.

Enrollment

Patients interested in participating in the study will be scheduled for a one-hour in-person appointment at the clinic site, where they will be asked for consent for participation in the study. The informed consent process will be completed by the study coordinator or a study pharmacist, (all who have successfully passed CITI training) in a face-to-face session with the patient. The pharmacist will explain the consent form in detail, with opportunities along the way for the patient to ask questions. The pharmacist will check, at proper points, for confirmation of understanding.

6. INTERVENTIONS

Devices

- Smart Phones with Apple Health Software will be used to monitor blood pressure once a day, and results will be sent automatically to the patients EHR (Epic)
- The Omron 10 Series Wireless Upper Arm Blood Pressure Device will be given to the patient to monitor blood pressure at home daily

Pre- and Post-surveys

- A pre- and post-survey will be given at the initial and final in-person appointments, respectively
- These surveys will collect basic patient demographics, knowledge of blood pressure, comfort with checking blood pressure at home, and previous experience working with a pharmacist

Pharmacist Management

- Review of evidence-based therapy and recommendations for improvement if needed
- Educate the patients on how to monitor their blood pressure with their Bluetooth enabled home blood pressure monitor and smart phones

- Patients will be scheduled for a one-hour in-person appointment for the initial study visit where informed consent will be obtained, and for the final study visit
 - At the final study visit, the patients will complete a post-study survey and be given a \$25 gift card upon return of the blood pressure device
- Review results once per week
 - If any patient has an SBP reading > 160 mmHg or DBP > 100 mmHg, they will be instructed to wait five minutes and then recheck their BP. If the BP readings exceed these thresholds for three days in a row, the patients should contact their primary care provider in the clinic for further management.
 - If SBP > 180 mmHg and/or DBP > 120 mmHg, patients will be instructed to call 911 or have someone drive them to the ER immediately
 - There will not be alerts sent to the study pharmacists if the blood pressure readings are above these thresholds
- Follow-up with patients once per week for six (6) weeks via scheduled 20-minute telehealth appointment with each patient via the HIPAA secure and compliant platform, VSee
 - During this telehealth appointment, the study pharmacists will counsel the patients on their blood pressure readings for that week and provide lifestyle education focusing on patient-specific diet and exercise recommendations
- The total duration of the study will be eight (8) weeks

